STUDY PROTOCOL

Effectiveness of custom-made foot orthoses vs heel lifts in children with Calcaneal Apophysitis (Sever disease): a randomized controlled trial

Date: 04-15-2018

Scientific Background

Calcaneal apophysitis (Sever disease) is a very common ailment present in the heel of children between 7 and 15 years old (1–5). Modern literature describes calcaneal apophysitis as a syndrome caused by overuse, resulting from the production of repetitive micro-traumas (3). Mechanical etiology relates the injury to the traction forces of triceps surae and plantar fascia on the calcaneus bony surface (3–6). The anatomical unit named ACPS describes the functional connection between the Achilles tendon, the calcaneus bone and the plantar fascia (6). There, the posterior trabecular calcaneal system works as a sesamoid bone between the fascia and the tendon fibers (6). Therefore, repetitive stress of the Achilles tendon and the plantar fascia is transmitted on the calcaneus surface affecting bone remodeling: creating perpendicular fibrous bands of cartilage in the secondary ossification center of the calcaneus (7). All this, in addition to repetitive impacts on the bony surface constitutes the focus of Sever's disease (5–8).

Sever disease, fortunately, is a benign ailment which disappears without exception after puberty when the secondary ossification center of the calcaneus is closed (9). Unfortunately, nowadays no evidence-based treatments are available (10). Nevertheless, conservative ones are the most commonly used; these include: sport activity modification, stretching and strengthening exercises and the application of podiatric strategies (heel-lifts and foot orthoses) (5,9–12).

Conservative strategies described in the foregoing paragraph are widely popular (10), but present a number of handicaps. Activity cessation means an increase of sedentary lifestyle, which is a major factor in obesity (13). The prescription of “off-the-shelf” heel-lifts is very widespread (9–12). These reduce pain levels because they elevate the heel, shortening distances between the triceps surae muscle and its insertion on the calcaneus (12). Unfortunately heel-lifts do not act completely on the mechanical etiology of Sever disease: ACPS traction and repetitive impacts (3,6,8). Heel-lifts only act on Achilles tendon traction, but lose both the effect of the plantar fascia and dissipating the impacts on the bony surface of the calcaneus (8,9).

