Following this line, there are some studies in literature that have used orthoses to act both on ACPS and the repetitive impacts (8,11,12,14–16). Orthoses provide support in the medial arch (relaxing plantar fascia), include a heel-lift component and a wider support surface (dispelling impacts) (8,11,12,14–16). The available evidence reported the use of orthoses (8,11,14), but most of them were prefabricated and the studies reveal statistical analysis and methodological

concerns that limit the validity of the results reported (9,16,17). Nor studies have previously compare the use of “off-the-shelf” with custom-made orthotics (16).

Objective

The present research wanted to provide a pragmatic randomized controlled trial with an intervention period of 12 weeks, with the aim to compare heel pain perception in children with calcaneal apophysitis using a custom-made Ethyl Vinyl Acetate foot orthoses and “off-the-shelf” heel lifts. Therefore, it was hypothesized that the primary outcome, pain relief, would be significantly improved with the custom-made orthosis compared to the heel lift.

Design

The study was a parallel-group, randomized controlled trial with concealed allocation, blinding of investigators and assessors and intention-to-treat analysis. It examined the effect of custom-made foot orthoses and heel lifts in children with calcaneal apophysitis. Participants were enrolled at the time of Sever disease diagnosis. After baseline assessment, children were individually randomized to “custom-made foot orthoses” (experimental group) or “off-the-self heel lifts” (control group). Concealed allocation was carried out by having randomization performed by a third party who was not involved in the recruitment and treatment of the children. Eight permuted blocks were used to stratify randomization by BMI (20 versus > 20 kg/m 2), Lunge Test (35 versus $> 35^\circ$ of dorsal flexion), FPI (4 versus > 4) and by VAS score (74 versus > 74 mm) because these were considered as important risk factors associated with pain severity in Sever disease (2,14,18,19). A researcher who was unaware of the randomized group allocation measured the outcomes at baseline and 12 weeks later. The design of the present research was based on and executed according to the CONSORT Statement. The study was approved by the Ethics Committee of Clinical Research of Aragón (C.P.-C.I.PI16/0303)

Participants

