All children with Sever disease diagnosis who came for an orthopaedic treatment at Podoactiva Headquarters Podiatric Clinic between September 2015 and April 2018 were assessed for study eligibility prior treatment application. Inclusion criteria included boys and girls between 9 and 12 years old diagnosed radiologically with calcaneal osteochondritis (10). Children were excluded if they: had suffered some trauma on the heel in the past 2 months; had received anti-inflammatory drugs and/or physical treatment for pain in the past 3 months; had presented

physical or neurological impairment; or were not interested. Informed consent form with parents' and children authorization was required to be part of the study.

Interventions

Before treatment application, all children received the following information about conservative strategies for pain reduction: triceps surae stretching, sport activity intensity reduction but no cessation and 10 minutes of ice application when pain exacerbation (10).

Each intervention (custom-made foot orthoses and heel lifts), consisted of a treatment period of 12 weeks. Both interventions were prescribed, designed and fabricated by a Podiatrist expert in orthopaedics, who was unaware of the randomized group allocations.

Experimental group

Children in the experimental group received as treatment intervention custom-made polypropylene foot orthoses (Podoactiva®, Spain). They were advised pragmatically to wear the orthoses at least 8 to 10 hours per day for the daily life and during sport activity.

Control group

Children in the control group received as treatment intervention an 8 mm "off-the-shelf" heel lift (Podoactiva®, Spain). They were advised pragmatically to wear the heel lifts at least 8 to 10 hours per day for the daily life and during sport activity.

Children were blinded to group allocation. Regardless to experimental or control group they received the same attention during the consultation and they were informed that the intervention given was adequate for their disease, before treatment application and after the follow-up.

Outcome measures

All the outcomes were obtained by an experienced and trained assessor who was blinded to group allocation. At baseline participant's weight and height were measured during each session with an Año-Sayol scale and stadiometer, respectively (Año-Sayol SL, Barcelona, Spain).

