The primary outcome was Sever disease pain perception, which was determined by three ways: VAS, algometry and by the following question: "Do you have pain at sport activity?" which had

to be answered by YES or NOT (Sport Activity Pain dependent variable). The VAS is commonly used to measure pain perception (20), and has been used before to measure pain perception in children with calcaneal apophysitis (14,19). The VAS is described as a horizontal line 100 mm in length where at each end points the words “No pain” and “Worst imaginable pain” are placed (18,20). Participants were asked to mark the line at the point which best represents the level of pain intensity that they were experiencing (14). Algometry is commonly used to measure pressure-pain threshold (21). To perform the algometry, the Wagner FPX™ 25 Algometer (Wagner Instruments®, USA) was used. It had been used before in children with calcaneal apophysitis (10). To perform the algometry children were asked to lie down in prone position on the stretcher, with knee and ankle bent 90°. Then the algometer was positioned on the Achilles tendon insertion on the calcaneus. Three separate measurements were obtained and the average of them was taken as algometry value (10).

Secondary outcomes were to determine the values of the FPI and the Lunge Test in the children with Sever disease. The FPI was performed following the guidelines of Redmond et al (22). FPI is a 6-point tool for clinical assessment, which evaluates the multisegmental nature of foot posture in the three spatial dimensions. Each component of the test is graded between -2 and +2 (signs of supination or pronation), where neutral is graded with 0. Finally, a score range from -12 (highly supinated) to +12 (highly pronated) is obtained (22–24). Lunge Test is commonly used to determine shortness in triceps surae muscle (2,24). Restriction in the length of this muscle is considered when the dorsal flexion of the ankle is less than 38-35° (2,5,23,24).

Statistical analysis plan

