Sample size estimation was based on the detection of a difference of 29% in the number of children with pain; and a mean difference of 0.39 or superior for the algometry and the VAS, between baseline and after the follow up based on a previous pilot study (2). Assuming a two-side α of 0.05, power of 80%, and a 10% drop-out rate, a sample size of 198 participants was required. Continuous variables were expressed as mean \pm standard deviation (SD) whereas qualitative variables were expressed as frequencies and percentages. Continuous data were checked for normality by Kolmogorov-Smirnov Test.

The baseline characteristics of the children were summarized using descriptive statistics and tabulated for comparison between intervention groups. Baseline characteristics were compared between included and excluded participants to analyze whether they were representative. Mann-Whitney U and T-Student Tests were used to compare continuous variables and the Fisher Test to compare dichotomous variables.

Differences between baseline and final assessment were performed using the average-to-average method. Mann-Whitney U Test was used to compare absolute and relative changes in algometry and VAS. McNemar Test was applied to calculate the improvement, which was positive when subjects changed from pain situation to no pain situation for the dependent variable Sport Activity Pain. Identifying treatment effectiveness after the follow-up was made by regression models. Linear regression was applied to quantitative variables, algometry and VAS, and logistic regression to dichotomous qualitative variables, association was measured in terms of odds ratio.

Statistical analysis of the outcomes was performed according to intention-to-treat principles compared the groups regarding pain perception evolution. For all tests, a two-sided p-value <0.05 was considered significant. The statistical analyses were performed using the SPSS software 22.0 for Windows (SPSS Ibérica, Madrid, Spain).

REFERENCES

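### The sport-pain question has no recall window, no record of sport participation and no rule for children not playing, so pain-related avoidance can be counted as improvement

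*Combined protocol and SAP*

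**What the plan says.** The Outcome measures section determines the primary outcome, pain perception, in three ways: VAS, algometry and the question "Do you have pain at sport activity". The answer has "to be answered by YES or NOT (Sport Activity Pain dependent variable"). No third option is offered, and no period is given to which the answer refers.

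The Statistical analysis plan section applies McNemar's test to this variable. Improvement is "positive when subjects changed from pain situation to no pain situation for the dependent variable Sport Activity Pain". That definition sets no condition on whether the child was doing sport at either visit. Logistic regression with an odds ratio then gives the treatment comparison.

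Outcomes were "measured the outcomes at baseline and 12 weeks later" (Design section). Under Interventions, every child is advised "sport activity intensity reduction but no cessation". The Scientific Background lists "sport activity modification, stretching and strengthening exercises and the application of podiatric strategies" among the usual treatments and discusses stopping activity as a drawback.

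Entry rests on "Inclusion criteria included boys and girls between 9 and 12 years old diagnosed radiologically with calcaneal osteochondritis". Neither pain at sport nor current sport participation is required. Nothing in the documents records participation or says how to score a child who is not playing.

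**The concern.** The question has a clear meaning only for a child who is doing sport. Suppose a child answers yes at baseline, then stops or avoids sport because the heel still hurts, and at 12 weeks answers no. That answer is literally correct, and the rule counts the child as improved. Without a participation record, nobody can find or correct this afterwards.

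The protocol itself recognises stopping sport as something these children do and advises against it, but does not measure it. Stopping happens after randomisation and may depend on how well the device works, so randomisation does not balance it. At stake are the within-arm improvement tested by McNemar and the between-arm odds ratio.

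**Working it through.** **Inputs from the plan.** The Statistical analysis plan section gives N = 198, 10% drop-out, two-sided alpha 0.05, 80% power, and a 29% difference in the number of children with pain. Assuming 1:1 allocation (no ratio is stated), evaluable children per arm = 198 × 0.90 / 2 = 89.1, taken as 89.

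**The plan's own figure.** A 29-point difference between two proportions needs at most 46 per arm over the base rates tried, or 103 in total after drop-out (53 per arm and 118 in total with continuity correction). A difference of 0.39 with an assumed SD of 1 needs 104 per arm, or 232 in total. The stated 198 would need an SD of about 0.93. Base rates and SD are not given, so 198 can be neither reproduced nor called wrong. The present point does not depend on it.

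**Assumptions.** The documents give no pain rates and no avoidance rates.
- True sport pain at 12 weeks is set at 64.5% on lifts and 35.5% on orthoses. This centres 29 points on 50% and reads the 29% as a between-arm contrast, although the text describes a difference between baseline and follow-up.
- Let a be the share of still-painful children who avoid sport and answer no.

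**Formulas.**
- Recorded pain rate = true rate × (1 − a).
- Power = Φ[(d − 1.96 × SE0) / SE1], where d is the recorded difference, SE0 = √[2p̄(1 − p̄)/89] with p̄ the mean of the two recorded rates, and SE1 = √{[p1(1 − p1) + p2(1 − p2)]/89}.

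**One line in full (20% on lifts, 5% on orthoses).** 0.645 × 0.80 = 0.516; 0.355 × 0.95 = 0.337; d = 0.179. SE0 = 0.0741 and SE1 = 0.0729. (0.179 − 1.96 × 0.0741)/0.0729 = 0.46, so power = 0.68.

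| True pain, lifts / orthoses | a, lifts / orthoses | Recorded pain | Difference (points) | Odds ratio | Power |
|---|---|---|---|---|---|
| 64.5% / 35.5% | 0 / 0 | 64.5% / 35.5% | 29.0 | 0.30 | 98% |
| 64.5% / 35.5% | 20% / 20% | 51.6% / 28.4% | 23.2 | 0.37 | 89% |
| 64.5% / 35.5% | 20% / 5% | 51.6% / 33.7% | 17.9 | 0.48 | 68% |
| 64.5% / 35.5% | 30% / 10% | 45.2% / 32.0% | 13.2 | 0.57 | 44% |
| 64.5% / 35.5% | 10% / 30% | 58.1% / 24.9% | 33.2 | 0.24 | over 99% |
| 50% / 50% | 10% / 30% | 45.0% / 35.0% | 10.0 (true 0) | 0.66 (true 1) | 27% false rejection |

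Equal avoidance shrinks the risk difference by the factor (1 − a). Unequal avoidance can shrink it, enlarge it, or create a difference where none exists.

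**Baseline.** Only a child who answered yes at baseline can be scored as improved. A child already avoiding sport at entry may answer no, cannot then improve, and may look worse on returning to sport. The misclassification therefore acts at both visits.

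**The case against.** The strongest reply is that the plan never says what a non-playing child answers. The question is general and in the present tense, and a child who avoids sport because it hurts could well answer yes. This stands. A reader might infer that the scoring rule itself gives the wrong value for such children. The documents support only that it can.

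A reader might also infer that the bias runs against the orthosis and could reverse the result. The documents do not support a direction. Both arms receive the same advice on sport, children are described as blinded, and avoidance by arm is unknown. Reversal from the rates assumed here would need more than 1 − 0.355/0.645 = 45% of still-painful children on lifts to answer no, with none on orthoses.

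Three further replies stand in part:
- The advice against stopping makes full cessation less likely, but advice does not guarantee adherence over 12 weeks.
- With equal 20% avoidance, power is 89%, still above the planned 80%. Dilution alone may cost little in power, though the estimate is still too small.
- VAS and algometry do not require the child to be playing, so they can show continuing pain. They do not correct the binary measure, which has its own McNemar and logistic analyses and its own 29% target in the sample-size statement.

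**Conclusion.** The point holds as a risk of misclassification in one of three primary measures. The plan gives no recall window, no participation record and no rule for children not playing. Pain-related avoidance can therefore be scored as improvement and could not be detected later.

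Within-arm improvement can be inflated. The between-arm effect can be diluted, hidden or exaggerated. In the illustrations, a true 29-point difference is recorded as anything from 13 to 33 points, and a true null is rejected about 27% of the time at avoidance of 10% and 30%. These sizes rest wholly on assumed pain and avoidance rates, on 1:1 allocation, and on reading 29% as a between-arm contrast. They show what is possible, not what happened. This is a cheap improvement to the measure and does not invalidate the trial.

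**What to change.** At baseline and at 12 weeks, ask whether the child did sport within a defined recall window and, if not, whether heel pain was the reason. In the Statistical analysis plan section:
- score stopping or avoiding sport because of heel pain as pain present, and so not improved;
- record no sport for other reasons separately, and do not count it as improvement;
- report sport participation by arm at both visits;
- add a sensitivity analysis using the raw yes/no answer.

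The cost is a short additional question at each existing visit, a scoring sentence and one extra analysis. No treatment or procedure changes.

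The Participants section gives recruitment up to April 2018, the text is in the past tense, and reference access dates run to April 2019, so the 12-week visits may already be complete. In that case, state the limitation when reporting this outcome, and do not interpret the binary measure without VAS and algometry.

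### The stated 80% power at 198 children is not supported for the between-arm VAS and algometry comparison: the 0.39 is worded as a before-to-after difference, and the stated inputs do not return 198

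*Combined protocol and SAP*

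**What the plan says.** All references are to the combined protocol and SAP.

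- **Sample size (Statistical analysis plan section).** Two effects are named, both attributed to a pilot study. The continuous one is "a mean difference of 0.39 or superior for the algometry and the VAS, between baseline and after the follow up". The binary one is stated separately, as "a difference of 29% in the number of children with pain". With two-sided alpha 0.05, the section continues: "power of 80%, and a 10% drop-out rate, a sample size of 198 participants was required".
- **Not given.** The section gives no SD, unit, base rate, baseline correlation or allocation ratio. It does not say which endpoint or test produced 198.
- **Hypothesis (Objective section).** Pain relief "would be significantly improved with the custom-made orthosis compared to the heel lift".
- **Analysis (Statistical analysis plan section).** The intention-to-treat analysis "compared the groups regarding pain perception evolution". For the continuous measures, "Mann-Whitney U Test was used to compare absolute and relative changes in algometry and VAS". In addition, "Linear regression was applied to quantitative variables, algometry and VAS, and logistic regression to dichotomous qualitative variables". No covariate is listed.
- **Comparator (Scientific Background section).** Of heel lifts the document says "These reduce pain levels because they elevate the heel", so the control arm is expected to improve as well.
- **Role of the measures (Outcome measures section).** VAS, algometry and a yes/no question on pain at sport together form the primary outcome. VAS is a 100 mm line; algometry is a pressure threshold.

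**The concern.** A change from baseline to follow-up and a difference between arms are different quantities. When both arms are expected to improve, the size of the change within an arm does not indicate how far apart the arms will be. The sentence describes the first quantity, while the trial tests the second.

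In addition, one unitless 0.39 serves two instruments on different scales, and no SD accompanies it. A reader cannot rebuild 198 from what is stated and cannot tell what between-arm difference 198 children could detect. If VAS or algometry shows no difference between arms, the 80% on record invites the conclusion that a comparison planned at that power came out null. The text does not establish that.

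**Working it through.** **Inputs from the plan:** two-sided alpha 0.05, power 80%, drop-out 10%, N = 198, effects 0.39 and 29%. **Assumptions, because the plan is silent:** 1:1 allocation; SD = 1 where 0.39 is read as standardised; normal data, with Mann-Whitney efficiency 0.955; event rates as shown. Normal quantiles are 1.960 and 0.842, and (1.960 + 0.842)² = 7.849.

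**Evaluable children.** 198 × 0.9 = 178.2, so about 178, or 89 per arm.

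**1. Attempts to reproduce 198 from the stated inputs**

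- *0.39 as a standardised between-arm difference.* n per arm = 2 × 7.849 / 0.39² = 15.70 / 0.1521 = 103.2. The exact t-test calculation gives 104.2, so 105 per arm; 210 / 0.9 = 233.3, about 234 randomised. For Mann-Whitney, 104.2 / 0.955 = 109.1, so 110 per arm; 220 / 0.9 = 244.4, about 245.
- *0.39 as a standardised paired change, which is the literal wording.* n = 7.849 / 0.1521 = 51.6, or 53.6 by paired t-test, so 54 in total. If required in each arm, 108 / 0.9 = 120.
- *29% as an absolute between-arm difference, least favourable rates 0.645 v 0.355.* n per arm = [1.960 × √(2 × 0.5 × 0.5) + 0.842 × √(0.645 × 0.355 + 0.355 × 0.645)]² / 0.29² = 45.5, so 46; 92 / 0.9 = 102.2, about 103.

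None of these gives 198. Drop-out applied as N × 1.1 does not rescue the standardised between-arm reading either (232 by t-test).

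**2. What does give about 198**

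Each route needs a figure that the plan does not state, or alters one that it does:

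- A raw between-arm 0.39 with SD about 0.92.
- A relative 29% fall from a rate near 70%: 0.705 v 0.501 gives 88.7 per arm, and 178 / 0.9 = 197.8.
- 0.39 SD with baseline adjustment and a correlation r of about 0.38 between baseline and the outcome analysed: 103.2 × (1 − 0.38²) = 88.3 per arm.
- A standardised 0.40 with no drop-out: 15.70 / 0.16 = 98.1, so 99 per arm.

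**3. Power at 89 per arm if 0.39 is a standardised between-arm difference**

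The noncentrality is 0.39 × √(89/2) = 2.60. Power is 73% by t-test and 71% by Mann-Whitney. If 198 was built as 180 × 1.1, 90 per arm give 74% by t-test. With no drop-out at all, 99 per arm give 78% and 76%.

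**4. Power at 89 per arm if 0.39 is a raw between-arm difference (t-test)**

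| Assumed SD | Power |
|---|---|
| 0.5 | 99.9% |
| 0.75 | 93% |
| 0.92 | 80% |
| 1.0 | 73% |
| 1.5 | 41% |
| 10 (for example, if in mm) | about 6% |

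**5. What 89 per arm detects with 80% power**

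- *Change in VAS or algometry:* (1.960 + 0.842) × √(2/89) = 0.420 SD; 0.422 by exact t-test; 0.422 / √0.955 = 0.432 by Mann-Whitney.
- *Sport Activity Pain, least favourable rates, normal approximation:* 0.605 v 0.395 needs 87.8 per arm, so about 21 percentage points. For an absolute 29 points, power at 89 per arm is about 98% on the same approximation.

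**The case against.** The strongest reply is that this is incomplete reporting and not an arithmetic error. The plan speaks of a mean difference, and a mean difference without an SD fixes no sample size. To say that the stated inputs fail to return 198 is then close to a tautology, and the 73% figure brings in an unstated input of its own, SD = 1. The curve is steep: an SD only about 8% smaller restores 80%. Baseline adjustment with a correlation of about 0.38 to 0.40 would do the same, and the plan does use linear regression. The before-to-after phrase may also be loose wording for a between-arm difference in change, since change is the variable that the Mann-Whitney test compares.

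Much of this stands. SD = 1 is an assumption, the wording is ambiguous, and the semicolon means that the phrase may not govern the 29% at all. But the reply does not supply the missing support. One value for both a 100 mm line and a pressure threshold makes sense mainly as a standardised effect, and on that reading 198 is too few for 80% without adjustment. Adjustment is possible, but no covariate is named. Several incompatible routes lead to 198, and the plan identifies none of them.

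Two stronger inferences are tempting. A reader might conclude that the trial is underpowered. The documents do not show that, because the SD and any baseline adjustment are unknown. A reader might also take the 6% row as the trial's true power, but nothing says that 0.39 is in millimetres, and the SD of 10 is only illustrative.

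**Conclusion.** The point holds in a limited form: the stated 80% power is not supported, as written, for the between-arm comparison of VAS and algometry. If 0.39 is a standardised between-arm difference, the unadjusted shortfall is modest: 71 to 73% power in place of 80%, or about 234 to 245 randomised in place of 198. If it is raw, the power cannot be determined without the SD. These figures rest on 1:1 allocation, 10% drop-out and no baseline covariate.

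The point does not extend to the whole trial. If the 29% is an absolute between-arm difference, 198 is more than enough for Sport Activity Pain. It should still be fixed, because the claim concerns two of the three primary pain measures and governs how a null result on them will be read.

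**What to change.** Keep 198 and leave the existing sentence on record. The recruitment window in the Participants section runs to April 2018, the month in which the document is dated, so a restated power is the useful change and a new sample size is not. Add a clarification, dated and labelled as later than the sample-size justification:

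> 198 randomised, about 178 evaluable (89 per arm, 1:1 assumed), two-sided alpha 0.05, gives 80% power for a between-arm difference in change of about 0.42 SD (t-test or unadjusted linear regression) or 0.43 SD (Mann-Whitney), smaller if baseline is adjusted for; and for about 21 percentage points between arms in Sport Activity Pain (least favourable rates, normal approximation).

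Alongside it, state:

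- the unit and SD of 0.39 for VAS and for algometry separately, so that 0.42 SD can be put into each instrument's own units;
- whether 0.39 is within or between arms;
- whether 29% is absolute or relative, and from what base rate.

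Where these cannot be recovered, say that they are unavailable. Only if 0.39 is confirmed as a standardised between-arm difference, add that unadjusted power for it is about 71 to 73%.

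The cost is one paragraph and possibly a less favourable stated power for VAS and algometry. It needs no extra children and no change to the analysis.

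### The effectiveness regressions name their outcomes but not the form of the outcome or any covariate, so adjustment for baseline and the four randomisation factors is not prespecified.

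*Combined protocol and SAP*

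**What the plan says.** In the Statistical analysis plan section, the between-arm comparison of change is a rank test: "Mann-Whitney U Test was used to compare absolute and relative changes in algometry and VAS". McNemar is named for Sport Activity Pain. It is a paired test, so it compares before with after and not one arm with the other. Effectiveness is then assigned elsewhere: "Identifying treatment effectiveness after the follow-up was made by regression models". The models are described in one sentence: "Linear regression was applied to quantitative variables, algometry and VAS, and logistic regression to dichotomous qualitative variables", with association reported as an odds ratio.

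The outcomes are therefore named. What is missing is whether VAS and algometry enter as 12-week value, absolute change or relative change, and which terms besides arm are in the model. Baseline data appear in the change measures, in the McNemar comparison and in a descriptive table: "The baseline characteristics of the children were summarized using descriptive statistics and tabulated for comparison between intervention groups". They are never named as a covariate.

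The Design section says "Eight permuted blocks were used to stratify randomization by BMI", and also by Lunge Test, FPI and VAS, each cut in two, because these are held to be risk factors for pain severity. No later section takes these four factors into an analysis.

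**The concern.** Randomisation was stratified on factors thought to predict pain, and VAS and algometry are measured at baseline and at 12 weeks. A model that uses this information normally gives a more precise treatment estimate at no cost in data. The plan does not commit to using it.

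Three things are at stake:

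- **Precision** for two of the three primary pain measures.
- **Calibration.** If stratified blocking balances prognostic factors and the analysis ignores them, the standard error is too large and the test is conservative.
- **Choice.** Several regressions fit the same text and differ in power. If the choice is made after results are seen, the chance of a false positive rises even though each test is sound on its own.

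**Working it through.** **The plan's own figure.** The inputs in the Statistical analysis plan are two-sided 5%, "power of 80%, and a 10% drop-out rate, a sample size of 198 participants was required", "a mean difference of 0.39 or superior for the algometry and the VAS, between baseline and after the follow up" and "a difference of 29% in the number of children with pain". No SD, unit, correlation or pair of rates is given, so 198 cannot be rebuilt. Reading 0.39 as a standardised difference, n per arm = 2(1.96 + 0.84)²/0.39², about 104. That is 208 in total, and 208/0.9 gives 232. A 29-point absolute difference needs 49 to 103 in total, depending on the rates.

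I therefore took the size as given. 198 × 0.9 = 178, or 89 per arm (1:1 assumed). The detectable difference is 2.80 × √(2/89) = 0.42 SD.

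**Assumptions.** Correlation r between baseline and 12 weeks of 0.3, 0.5 or 0.7, equal SDs at both visits, and normal outcomes.

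**Variance of each outcome form**, in single-visit SD²:

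- 12-week value: 1
- change: 2(1 − r)
- 12-week value adjusted for baseline: 1 − r²

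Adjusted over change is (1 + r)/2 = 0.65 / 0.75 / 0.85. So 178 adjusted children carry the information of 178/0.65 = 274, 178/0.75 = 237 or 178/0.85 = 209 analysed on change.

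**Power** = Φ(d√(89/2) − 1.96), with √(89/2) = 6.67. The plan's wording of the 0.39 can be read as a change, so both scalings are shown. If 0.42 is in change-score SDs, d is 0.42 for change, 0.42√(2(1 − r)) for the 12-week value and 0.42√(2/(1 + r)) when adjusted. If it is in single-visit SDs, d is 0.42/√(2(1 − r)), 0.42 and 0.42/√(1 − r²).

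| Power, % (r = 0.3 / 0.5 / 0.7) | Change-score SDs | Single-visit SDs |
|---|---|---|
| Regression on change | 80.0 / 80.0 / 80.0 | 65.8 / 80.0 / 95.1 |
| Regression on 12-week value | 91.2 / 80.0 / 58.3 | 80.0 / 80.0 / 80.0 |
| Adjusted for baseline | 93.5 / 89.9 / 86.0 | 83.6 / 89.9 / 97.5 |

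Simulating the design (178 children, 2⁴ = 16 strata, blocks of 4 assumed) in change-score SDs gives about 82 / 82 / 80, 90 / 83 / 58 and 92 / 91 / 85%. Adjustment thus gains 10 / 9 / 5 points over regression on change and 2 / 8 / 27 over regression on the 12-week value. Which unadjusted form is better depends on whether r is above or below 0.5, which is unknown.

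**Where the gain comes from.** Mostly the baseline value. Adding BMI, Lunge and FPI gains nothing if they explain nothing more, and 0.5 to 3.0 points if they explain 10% of the remaining variance.

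**Unequal SDs.** With a follow-up to baseline SD ratio k, adjusted over change is k²(1 − r²)/(1 + k² − 2rk). At k = 1.4 and r = 0.7 this is 1.96 × 0.51/1.00 = 1.00, so nothing is saved over change.

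**Non-normal residuals.** With t (3 df) and lognormal residuals the adjusted regression still beat both unadjusted regressions. Across all settings run, normal ones included, the margin was about 1 to 27 points. Against Mann-Whitney on change it gained about 3 to 20 points with normal data. At r = 0.5, Mann-Whitney led by 92 to 90% with t (3 df) and by 99 to 90% with lognormal residuals.

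**Type I error (simulated).** Mann-Whitney on VAS change rejects 2.5 to 4.0% with working 16-stratum blocks and 4.4 to 5.1% without stratification. The adjusted model rejects 4.2 to 5.4%. Counting a success if any of five readings is significant (Mann-Whitney on absolute or relative change, regression on change, regression on the 12-week value, adjusted regression) gives about 7 to 8% with stratification and 10 to 12% without.

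**Sport Activity Pain.** At a 29-point difference, power is already 97.6 to 99.5% unadjusted (control rates of 45 to 75% assumed). Adjustment adds less than 1 point.

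**The case against.** The strongest reply is that this is a gap in reporting. The outcomes are named, effectiveness is assigned to regression, and nothing forbids covariates. That stands: a reader might infer that the plan rules out adjustment or discards baseline, and the text supports neither. Adjustment is left open, and baseline does enter through the change scores.

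A second reply is that Mann-Whitney is a reasonable choice for pain data. The plan foresees a normality check, and with heavy tails or skew the rank test can be the more powerful. That also stands. A reader might infer that Mann-Whitney should be dropped, or that its 3 to 20 point deficit with normal data is the price of omitting covariates. Neither follows. That gap mixes rank testing with lack of adjustment, and the plan gives effectiveness to regression, so the relevant comparison is with the unadjusted regressions.

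A reader might also infer that ignoring the stratification makes the tests invalid. It does not: each unadjusted test is conservative or close to nominal. False positives become an issue only through choice among models.

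Finally, every size here is driven by assumptions. SD, r, block size and factor effects are not in the documents. The conservatism in particular assumes 16 working strata, while the Design section speaks of eight permuted blocks.

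**Conclusion.** The point holds as a gap in specification that should be closed. The plan fixes neither the form of the linear outcome nor any covariate, and no stated analysis uses the four randomisation factors. Against the unadjusted regressions that the text allows, adjustment was better in every setting simulated, by roughly 2 to 27 points of power with normal data and equal SDs in change-score units. The gain over regression on change can fall to zero if SDs rise at follow-up, and the gain over Mann-Whitney is not assured with non-normal outcomes. For Sport Activity Pain the gain is negligible. The direction against unadjusted regression is secure; the size is not, because r and the SDs are unknown. The validity of any single planned test is not in question.

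**What to change.** Write out the regressions already planned:

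- **VAS:** 12-week VAS on arm, continuous baseline VAS, and BMI, Lunge and FPI as the two-level randomisation factors. Continuous baseline VAS replaces its own stratum.
- **Algometry:** 12-week algometry on arm, continuous baseline algometry and all four two-level factors.
- **Sport Activity Pain:** logistic regression on arm and the four factors, fixed in advance and not chosen from observed counts. State that the odds ratio is conditional on the covariates. With the assumed rates the smaller outcome class averages 54 to 80 children, or 11 to 16 for each of five terms.

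Report adjusted differences with 95% CIs and name these models as the ones that decide. Keep the Mann-Whitney comparisons of absolute and relative change as supporting analyses.

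The change needs no new data, only a few lines of SAP text and a few model terms in the software already named. The downside is the extra terms and reliance on a linear model if outcomes are strongly non-normal. The Participants section has recruitment running to April 2018, the plan is in the past tense, and its references carry 2019 access dates. If outcomes had been seen before the model was fixed, it must be labelled post hoc, which limits its value as prespecification.
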